PRE-TESTS: Before and after the INTERVENTION, we will conduct high-resolution phenotyping of subjects which will include: lab-based hemodynamic tests of vascular function; blood-based biomarkers related to cardiovascular health; 24-h urine collection; 24-h food/beverage log; 24-h ambulatory blood pressure recording; VO₂peak fitness test. These are detailed below *Specific Experimental Approaches*.

ASSIGN: Subjects will be randomized to either the heat therapy group or exercise training group, then undergo 30 sessions of the specific intervention at a rate of 3-4 per week over an 8 to 10-week period. Randomization will be stratified by age and sex to ensure equal numbers within each stratum. Further stratification, for example by BMI or initial blood pressure, would be difficult given the small sample size. (More details of the randomization process are under *Randomization*). After the first 15 sessions, subjects will be re-tested for hemodynamic and biomarker adaptations to the intervention (INTERIM-TEST). After 30 sessions, subjects will undergo final POST-TESTS.

INTERVENTION: Subjects in the **heat therapy** group will report to the lab to undergo heat therapy sessions 3-4 times per week, with 45 minutes of hot water immersion per session. The goal of heat therapy is to maintain core temperature above 38.5°C for at least 30 min. This target has previously been shown to be the threshold temperature and time exposure to optimize adaptations to passive heat exposure¹¹. Subjects in our lab, including sedentary, hypertensive, obese, and spinal cord-injured subjects, have tolerated this heating protocol very well. Subjects will be checked for euhydration prior to entering the tub and will be monitored closely throughout heating for heart rate and blood pressure during all sessions. In addition, core temperature (T_{core} ; FDA approved ingestible core temp sensing pill; Accutemp Temperature Monitoring System by HQ Inc.) will be monitored during the first 5 and final sessions whereas aural temperature may be monitored in all sessions. Subjects will be removed from the hot bath if T_{core} exceeds 39.5°C. Water immersion is the preferred method of heating since it is capable of increasing core temperature and heart rate at a rate similar to moderate-intensity exercise¹². Subjects in the **exercise training** group will report to the lab for a supervised exercise training session 3-4 times per week. We will use heart rate

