subject is having blood drawn as part of a medical exam, they will be asked to inform their medical provider that they provided blood about equal to that of a standard donation. The magnitude of severity for risks of infection or syncope from the blood sampling is very low, and the probability of these risks occurring is very low. Bruising is temporary and does not pose any long-term risks to the subject, aside from mild discomfort. Pressure will be applied to the site after removal of the needle to assure that any bleeding ceases quickly. A band-aid and/or small gauze pressure wrapping will be applied to the subject's arm to keep the site protected. The risk of infection at the site is low. The subject will be instructed on how to keep the site clean during the days following the study. The probability of the adverse reactions discussed above is low, and the severity is low.

Subject Rights and Withdrawal. Taking part in this research is a voluntary decision made by the research subject. The subjects can stop at any time and their decision whether or not to participate will not affect their relationship with the University of Oregon. By partaking in this research, subjects do not waive any liability rights for personal injury. The investigators may stop a subject from taking part in this study at any time if it is in their best interest, if the subjects do not follow the study rules (e.g., compliance of less than 70% for heat or exercise sessions, or failure to follow study guidelines despite several reminders), or if the study is stopped. For example, if the investigators determine the study is overly stressful for the subject (as indicated by body language and an extremely elevated heart rate and/or blood pressure) they may stop the subject from participating in the study. Or, if subjects express pain or discomfort beyond what is normally expected, the investigators will stop the subject from participating in the study.

Emergency Procedures. In the unlikely event of a medical emergency, we will follow the "Guidance for Human Physiology Investigators on Emergency and Non-Emergency Procedures for Human Subject Research," approved previously by the IRB. In addition, we would provide responding emergency healthcare providers with the MEDICAL HISTORY FORM provided by the subject.

As this human subject research meets the definition of Clinical Trial, we have attached our DATA AND SAFETY MONITORING PLAN.

Protocol 2:

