**Specific Aim 1:** These studies in mid-life adults will determine if heat therapy can be used to improve cognitive aging and dementia risk, with potentially important clinical implications for the prevention of ADRD. Demonstrating that heat therapy can be used as a novel treatment for essential hypertension is timely and important as there is a clear need for alternatives to exercise training and pharmacological approaches. As HTN is linked to ADRD risk, these studies will allow us to link outcome measures in Protocol 1 (focused on CVD risk) with Protocol 2 (focused on ADRD risk) before and after subjects undergo heat therapy or exercise intervention in Protocol 1. The proposed studies are innovative and include an intention-to-treat randomized clinical trial and detailed high-resolution phenotyping to better understand the improvements in blood pressure regulation following heat therapy. *Overall, this work advances a novel treatment option for those with HTN and in the prevention of CVD and ADRD.*

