### 7.2 Analysis Populations

Intention-to-Treat will be the primary analysis approach. However, as one goal is to compare outcomes when subjects maintain compliance with heat therapy and exercise training, we will also employ per-protocol analysis as a secondary approach, including subjects with  $\geq 90\%$  compliance. As an exploratory step, we will conduct analyses of variance to compare characteristics of dropouts vs. completers, as this may inform future endeavors.

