## 8.4 Treatment Compliance

Compliance will be defined as participation in Heat Therapy or Exercise Training intervention visits.

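### Investigators may end study participation for attendance below 70%, and nothing supplied keeps those participants in outcome testing, so outcome loss can depend on adherence in an ITT trial

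*Protocol*

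**What the plan says.** Protocol Section G, Subject Rights and Withdrawal, states: "The investigators may stop a subject from taking part in this study at any time". One ground is failure to follow study rules, and "compliance of less than 70% for heat or exercise sessions" is given as an example of that. Best interest, undue stress and unexpected pain are covered in the same paragraph. SAP 8.4 adds: "Compliance will be defined as participation in Heat Therapy or Exercise Training intervention visits". Neither document gives the denominator for the 70% or the time at which it is judged.

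Under ASSIGN in Protocol Section C, participants are randomised and "then undergo 30 sessions of the specific intervention at a rate of 3-4 per week". The interim tests come after the first 15 sessions, and "After 30 sessions, subjects will undergo final POST-TESTS". No visit is fixed by calendar date for someone who stops sooner.

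SAP 4.1 says the studies "include an intention-to-treat randomized clinical trial", and SAP 7.2 says "Intention-to-Treat will be the primary analysis approach". SAP 7.2.1, headed as ITT or modified ITT, requires some intervention and at least one assessment after baseline. SAP 7.2 and 7.2.2 set up a secondary per-protocol analysis at 90% compliance or more. SAP 7.4 relies on mixed models for missing data and keeps multiple imputation for predictors and covariates. It asserts that bias is limited even when missing-at-random fails, but names no method for that case.

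**The concern.** An ITT comparison is informative because it includes outcomes from people who adhered poorly. The Section G power applies to taking part in the study, so on its face it ends outcome testing along with the sessions. The adherent-only question already has its own analysis.

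Unequal use of the power between arms is foreseeable. The protocol's own background says compliance with exercise training is commonly poor. Participants know their arm, and the blinding described covers data entry and preliminary analysis, not a decision to stop someone. If low adherers are lost more often in one arm, or differ more from completers there, the primary result moves towards a per-protocol result while still carrying the ITT label.

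**Working it through.** **1. What 70% means in sessions.** Inputs: 30 planned sessions (Protocol C), the 70% example (Protocol G) and the 90% cut (SAP 7.2.2). Assumption: all 30 sessions are the denominator.

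- 0.70 × 30 = 21, so below 70% means 20 or fewer attended, or 10 or more missed.
- 0.90 × 30 = 27, so per-protocol means 27 or more.

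**2. What each group contributes if the power is used and testing ends.**

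| Sessions attended | Tests reached | Protocol 1 analysis |
|---|---|---|
| 14 or fewer, stopped | Neither | Outside the ITT set of SAP 7.2.1 |
| 15 to 20, stopped | Interim possible; post not scheduled | In the ITT set, no post value |
| 21 to 26 | Attendance example not met | ITT, not per-protocol |
| 27 or more | Attendance example not met | ITT and per-protocol |

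In Protocol 2 there is no interim measurement, and SAP 9 uses the post-intervention value as the outcome. A participant stopped in either of the first two rows therefore contributes no outcome there.

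**3. The plan's allowance for loss.** Protocol C assumes 20% dropout: 50 × (1 − 0.20) = 40, which matches the 40 completers it asks for. That allowance is tied to the per-protocol analysis. It covers numbers, not who is lost, and the documents do not say how much of it would come from attendance stops.

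**4. Illustration of bias.** Let f be the fraction of an arm lost this way, and D the amount in mmHg by which their blood pressure fall would have been smaller than that of completers. The mean fall over everyone in the arm equals the completers' mean fall minus f × D. A completers-only difference (heat minus exercise) is therefore too large by

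f(heat) × D(heat) − f(exercise) × D(exercise).

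The values of D, and the use of f = 0.2 for this cause, are assumptions.

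- Loss in one arm only, f = 0.2: D = 2 gives 0.4; D = 4 gives 0.8; D = 6 gives 1.2 mmHg. Against the 4.0 mmHg target that is 10%, 20% and 30%. Loss in the heat arm flatters heat; loss in the exercise arm does the reverse.
- Equal f and equal D in both arms: 0.
- Unequal loss in both arms. Assume completers fall 9 mmHg with heat and 5 mmHg with exercise, and lost participants would not have responded, so D = 9 and D = 5. With 30% heat and 10% exercise lost: 0.3 × 9 − 0.1 × 5 = 2.2, so a true 1.8 appears as 4.0. With 10% and 30%: 0.1 × 9 − 0.3 × 5 = −0.6, so a true 4.6 appears as 4.0.

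These figures ignore interim data. The Aim 1 mixed model would use interim values from those stopped after session 15 and so reduce the shift, as far as missing-at-random holds.

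**The case against.** Several stronger readings are tempting, and the documents do not support them.

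- **That low attenders are removed by rule.** The protocol says investigators may stop a subject and gives the 70% figure only as an example. How often the power would be used is unknown.
- **That the plan contradicts ITT outright.** Section G governs conduct and SAP 7.2 governs analysis. SAP 7.2.1 openly allows a modified ITT set that needs one post-baseline assessment. This is a tension and an omission.
- **That everyone stopped is lost to the analysis.** Those with an interim test stay in the Protocol 1 mixed model (SAP 7.4 and 9), and SAP 7.2 plans to compare dropouts with completers.
- **That 0.8 mmHg is an estimate of the bias.** It rests on an assumed deficit and on assigning the whole 20% allowance to this cause in one arm. Equal loss and deficit in both arms give zero.

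A further limit is that the protocol refers to an attached Data and Safety Monitoring Plan, which was not supplied, nor were the consent forms. The absence of a provision means absence from the protocol and SAP text available here.

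What remains is that no available text separates stopping sessions from ending outcome tests. Mixed modelling does not repair loss that depends on unobserved response, and comparing dropouts with completers describes selection without correcting it.

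**Conclusion.** The point stands in limited form and should be addressed. The plan permits a loss of outcomes that depends on adherence. Early stops leave the ITT set, later stops lack a post value, and both contribute nothing to Protocol 2 outcomes. The size and direction of any bias cannot be determined from the documents. The range of 0.4 to 1.2 mmHg is conditional on f = 0.2 in one arm, D = 2 to 6 mmHg and a completers-only comparison. The session counts assume that the 70% refers to all 30 sessions. Confidence is moderate, because the power is discretionary and the monitoring plan is unseen.

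**What to change.** Reconcile Protocol G with SAP 7.2 and 7.2.1:

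- State that stopping solely for low attendance does not by itself end outcome testing. These participants are still invited to the interim and post tests at the planned calendar times, and stay in the ITT analysis unless they withdraw consent.
- Leave stops for best interest, stress, pain or other safety reasons to the investigators as now written. The same holds for whether any particular test, including the maximal exercise test, is appropriate for a given person.
- State the denominator and timing of the attendance figure.
- Record stopping of sessions and withdrawal from testing as separate events, and report both by arm with reasons.

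The SAP was updated in 2024 and SAP 8.2 already reports a deviation found during analysis, so visits may be complete. In that case a protocol sentence cannot recover data. Report by arm who was stopped for attendance and when, and add a sensitivity analysis for outcomes not missing at random.

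The cost is a short text change and, if visits continue, a few extra test visits paid at the rates Protocol D already sets for every participant. After completion it is one additional table and one additional analysis.

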## 2 Abbreviations and Definitions

ADRD	Alzheimer's disease and its related dementias
ASL	Arterial spin label
AE	Adverse Event
BMI	Body mass index
BP	Blood pressure
CA1, CA2, CA3	Corpus Ammons fields 1, 2, and 3
CRF	Case Report Form
CVD	Cardiovascular disease
ERC	entorhinal cortex
eTIV	estimated total intracranial volume
fODF	Fibre orientation distribution function
GM	Gray matter
HbA1c	Glycated hemoglobin
HDL	High-density lipoprotein
HTN	Hypertension
IMP	Investigational Medical Product
LDL	Low-density lipoprotein
LLD	Lower limit of detection
SAP	Statistical Analysis Plan
ULD	Upper limit of detection
WM	White matter
WMH	White matter hyperintensities

## 3 Introduction

### 3.1 Preface

#### Protocol 1:

In the United States, hypertension (HTN) accounts for more cardiovascular disease (CVD) related deaths than any other modifiable CVD risk factor, second only to cigarette smoking as a preventable cause of death for any reason. In fact, in 2010, high blood pressure was the leading cause of death and disability-adjusted life years worldwide. According to the CDC, about 75 million American adults (32%) have high blood pressure, and about 1 in 3 American adults have pre-HTN. Based on very recently published new guidelines on the prevention and management of hypertension by the American College of Cardiology/American Heart Association Task Force on hypertension, the percent of people in the United States with HTN are even higher with the new classification. Lifestyle and exercise interventions are considered a first-line preventative against the development of HTN and in the treatment of diagnosed HTN. Unfortunately, the vast majority of people are

reticent to initiate exercise training or have poor compliance. Additionally, some patient groups are not able to perform exercise due to a number of limitations or are not able to obtain the full benefits of exercise to lower CVD risk. Thus, alternative non-pharmacological options to lower blood pressure and improve CVD risk are critically needed. Heat therapy, in the form of hot bath or sauna, is an ancient practice that has recently regained attention in the prevention and treatment of CVD. A recent 20+ year prospective cohort study from Finland, in which sauna use is extremely common and part of the culture, has demonstrated that regular sauna use was associated with reduced risk of developing hypertension, which may have explained in part the reduced rates of all-cause cardiovascular deaths and reduced rates of Alzheimer's Disease and other memory-related disorders with regular sauna use previously reported in the larger cohort. We recently demonstrated in young, normotensive sedentary subjects that heat therapy in the form of hot water immersion lowered resting blood pressure and greatly improved numerous biomarkers of cardiovascular health including endothelial function and arterial stiffness. We have pilot data demonstrating that chronic heat therapy can improve blood pressure and numerous biomarkers of vascular function in people with HTN, potentially through a profound reduction in sympathetic neural outflow and improvements in arterial compliance. Furthermore, our preliminary data suggest improvements in blood pressure are greater than observed with the idealized standard of care, aerobic exercise training.

#### **Protocol 2:**

Protocol 2 will be performed within the experimental framework of Protocol 1 in a subset of study participants. Subjects are not able to undergo Protocol 2 without undergoing Protocol 1, as the heat therapy and exercise interventions are in Protocol 1. Subjects enrolled in Protocol 1 may elect to not participate in Protocol 2. Aging is associated with a gradual decline in cognitive function, which can affect quality of life and predisposes individuals to age-related neurodegenerative diseases, including Alzheimer's disease and its related dementias (ADRD). As the population of middle-aged and older adults is increasing rapidly, there is increasing need to understand the mechanisms of cognitive aging. Aging exerts direct effects on the heart that increase our susceptibility of developing CVD, including HTN. However, the largest portion of the marked increase in CVD risk with advancing age is driven by two highly interactive factors: increases in systolic arterial blood pressure (SBP) and vascular dysfunction. These events are responsible for many of the changes observed with aging, are key risk factors for other major clinical disorders, and are increasingly implicated in cognitive declines with aging and risk of ADRD. Importantly, it has been reported that the frequency of sauna bathing was associated with lowered risks of dementia and Alzheimer's disease. The results of these studies suggest that heat therapy may reduce the risk of hypertension and dementia either independently or through reductions in systolic blood pressure but are confounded by other factors such as greater sauna use by individuals with higher income, education and discretionary time. The effects of heat therapy on cardiovascular health and cognitive function are best determined by randomized clinical research trials. Notably, women were not included in previous studies, and we have substantial preliminary data demonstrating that women are showing all of the same benefits of heat therapy as men. Heat therapy represents a possible lifestyle intervention that, as our preliminary findings suggest, may be more effective in lowering systolic blood pressure and reducing arterial stiffness than aerobic exercise training, which is known to slow/delay the development of normal cognitive aging. Therefore, the purpose of Protocol 2 is to determine the potential of heat therapy in middle-life individuals with hypertension to improve cognitive function and MRI-based markers of ADRD risk.

### **3.2 Scope of the analyses**

#### **Protocol 1**

The overarching goal of this research is to perform a clinical trial to determine whether heat therapy improves blood pressure and vascular health in HTN.

## Protocol 2

The overarching goal of this research is to determine whether 30 sessions of heat therapy or exercise training (performed by subjects in Protocol 1) improves cognitive function (using the NIH Toolbox:<http://www.nihtoolbox.org>) and MRI-based markers of aging and Alzheimer's risk (using specific MRI-based biomarkers and tests).

## 4 Study Objectives and Endpoints

### 4.1 Study Objectives

#### Protocol 1

**Specific Aim 1:** Utilizing a prospective randomized clinical trial study design, we will determine whether heat therapy improves **blood pressure** (both in clinic and ambulatory) better than dynamic aerobic exercise, the gold-standard non-pharmacological treatment of essential HTN. Specifically, we hypothesize that 30 sessions of passive heat therapy using hot water immersion over 8-10 weeks will improve blood pressure in HTN individuals to a greater extent than 30 sessions of exercise training over the same time period.

**Specific Aim 2:** We will determine whether heat therapy will improve biomarkers of arterial health and compare responses to exercise training. We hypothesize that 30 sessions of heat therapy will improve arterial stiffness in HTN to a greater extent than exercise. Furthermore, we hypothesize key clinical biomarkers of systemic inflammation and oxidative stress will be improved following heat therapy.

**Specific Aim 3:** In an exploratory aim, we will determine whether the acute decreases in blood pressure following an initial heat therapy session or exercise peak test predict the sustained reduction in resting blood pressures following heat therapy treatment or exercise training in HTN. These findings would provide significant predictive information beyond baseline resting blood pressures. We hypothesize that the reduction in blood pressure following acute stressors will be predictive of treatment effects on resting blood pressure.

#### Protocol 2

**Specific Aim 1:** These studies in mid-life adults will determine if heat therapy can be used to improve cognitive aging and dementia risk, with potentially important clinical implications for the prevention of ADRD. Demonstrating that heat therapy can be used as a novel treatment for essential hypertension is timely and important as there is a clear need for alternatives to exercise training and pharmacological approaches. As HTN is linked to ADRD risk, these studies will allow us to link outcome measures in Protocol 1 (focused on CVD risk) with Protocol 2 (focused on ADRD risk) before and after subjects undergo heat therapy or exercise intervention in Protocol 1. The proposed studies are innovative and include an intention-to-treat randomized clinical trial and detailed high-resolution phenotyping to better understand the improvements in blood pressure regulation following heat therapy. *Overall, this work advances a novel treatment option for those with HTN and in the prevention of CVD and ADRD.*

### 4.2 Endpoints

In **Protocol 1**, the primary and secondary outcomes from the original grant were updated after interruption from the COVID-19 pandemic shut-downs led to not being able to collect originally planned Aim 2 outcomes: MSNA; FMD;  $\beta$ -stiffness index; Wall thickness, Dynamic arterial compliance; Reactive hyperemia; and Baroreflex sensitivity. In **Protocol 2**, The primary cognitive outcome is a memory domain composite score calculated as the average of age-corrected list-sorting and age-corrected picture sequence z scores. The primary brain biomarker of ADRD risk outcomes are arterial transit time variables mean perfusion in gray matter and mean

perfusion in white matter. The primary and secondary outcomes are shown by protocol and aim in **Table 1** below.

